4.3.4 Pirfenidone Background Treatment

The recommended dose of pirfenidone is 2403 mg/d (or 1800 mg/d for patients in Japan) administered in divided doses three times per day (TID) with food. Initial pirfenidone treatment should be titrated over 14 days, as tolerated, to the full dose of 9 capsules per day (three capsules TID), as follows:

- Days 1–7: one capsule TID
- Days 8–14: two capsules TID
- Day 15 and continuing: three capsules TID (maximum of 9 capsules daily)

Each dose should be taken with food, at approximately the same times each day. Patients will remain on a stable maintenance dose for the duration of the study period unless the dose is reduced to manage an AE. All doses of pirfenidone are to be taken with food to reduce the likelihood of gastrointestinal symptoms. The dose titration period of 14 days at the initiation of treatment is designed to maximize tolerability. Exposure to sunlight (including sunlamps and tanning beds) should be avoided to minimize the possibility of photosensitivity reactions or rash. Patients should be instructed to use sunscreens that have a sun protection factor (SPF) of 50 or higher as well as protection against ultraviolet A (UV-A) and ultraviolet B (UV-B) radiation. Guidelines for dosage modification and treatment interruption or discontinuation are provided in Section 5.1.4. For patients treated with PIRESPA (limited to Japan), dose titration and management of

adverse effects should be based upon guidance in the marketed product label including a maximum recommended dose ≤ 1800 mg/d (Costabel et al. 2014).

If a patient experiences significant side effects, treatment of symptoms and/or temporary dose modifications should be considered. The decision to modify pirfenidone dosing is ultimately the responsibility of the investigator; however, occasional day-to-day variability in dosing due to patient initiative and preference is expected to occur.

Patients who enter the pirfenidone titration run-in period will be monitored for a minimum of 4 weeks and up to 6 weeks after screening and prior to randomization, to allow for dose modifications due to tolerability issues and to limit the requirement for dose adjustment during the 52-week study period.

Any overdose or incorrect administration of pirfenidone should be noted on the pirfenidone administration eCRF. Adverse events associated with either an overdose or incorrect administration of pirfenidone should be recorded on the Adverse Event eCRF.

4.3.5 Investigational Medicinal Product Accountability

The investigational medicinal product (IMP) required for completion of this study (i.e., lebrikizumab and pirfenidone) will be provided by the Sponsor. Pirfenidone, licensed as ESBRIET or PIRESPA, may be locally sourced for patients with access through their healthcare provider until provided by the Sponsor as IMP through the IxRs system. The investigational site will acknowledge receipt of the IMP, using the IxRS to confirm the shipment condition and content. Any damaged shipments will be replaced.

The IMP will either be disposed of at the study site according to the study site's institutional standard operating procedure or be returned to the Sponsor with the appropriate documentation. The site's method of IMP destruction must be agreed upon by the Sponsor. The site must obtain written authorization from the Sponsor before any IMP is destroyed, and IMP destruction must be documented on the appropriate form.

Accurate records of all IMP received at, dispensed from, returned to, and disposed of by the study site should be recorded on the Drug Inventory Log.

4.3.6 Post-Study Access to Lebrikizumab and Pirfenidone

The Sponsor will offer post-study access to the study drug lebrikizumab and/or pirfenidone free of charge to eligible patients in accordance with the Roche Global Policy on Continued Access to Investigational Medicinal Product, as outlined below.

A patient will be eligible to receive study drug after the end of the study if all of the following conditions are met:

- The patient has a life-threatening or severe medical condition and requires continued study drug treatment for his or her well-being

- There are no appropriate alternative treatments available to the patient
- The patient and his or her doctor comply with and satisfy any applicable legal or regulatory requirements

A patient will not be eligible to receive study drug after the end of the study if any of the following conditions are met:

- The study drug is commercially marketed in the patient's country and is reasonably accessible to the patient (e.g., is covered by the patient's insurance or would not otherwise create a financial hardship for the patient)
- The Sponsor has discontinued development of the study drug or data suggest that the study drug is not effective for IPF
- The Sponsor has reasonable safety concerns about the study drug as treatment for IPF
- Provision of study drug is not permitted under the laws and regulations of the patient's country

The Roche Global Policy on Continued Access to Investigational Medicinal Product is available at the following location:

http://www.roche.com/research_and_development/who_we_are_how_we_work/clinical_trials/global_standards.htm.

4.4 CONCOMITANT THERAPY

4.4.1 Permitted Therapy

Concomitant therapy is defined as any medication (e.g., prescription drugs, over-the-counter drugs, herbal/homeopathic remedies, and nutritional supplements) used by a patient from 7 days prior to screening to the study completion/early termination visit. All concomitant medications should be reported to the investigator and recorded on the Concomitant Medications electronic Case Report Form (eCRF).

4.4.1.1 Corticosteroids

Chronic maintenance oral corticosteroid therapy, defined as daily or alternate day oral corticosteroid maintenance therapy is not permitted within the 4 weeks prior to screening Visit 1, during screening *and run-in*, or throughout the study period. Short-term treatment with corticosteroids (≤ 4 weeks) with subsequent corticosteroid dose tapering is permitted for patients who experience an acute IPF exacerbation as defined in Section 4.5.12.

4.4.1.2 Rescue Therapy

Patients in Cohort A who experience confirmed disease progression ($\geq 10\%$ decline in FVC [*mL/year; relative change*] or non-elective hospitalization) during the placebo-controlled study period will be allowed, at the investigator's discretion, to start rescue therapy, including use of pirfenidone or other IPF treatment provided that it is a therapy for IPF *approved* in the applicable region (e.g., European Union, Canada,

Mexico, Peru, or Japan). Patients who start rescue therapy will be allowed and encouraged to remain in the study and continue study treatment.

During the open-label lebrikizumab study period, at the investigator's discretion, a patient can initiate additional therapy for IPF that is approved in the applicable region (e.g., European Union, Canada, Mexico, Peru, or Japan) without evidence of disease progression.

Patients in Cohort B who experience a confirmed disease progression ($\geq 10\%$ decline in FVC [*mL/Year; relative change*] or non-elective hospitalization) during the placebo controlled study period should continue the study drug medication, including background pirfenidone. However, at the investigator's discretion, the initiation of rescue therapy that is approved by local regulatory authorities is allowed. Combination treatment with pirfenidone and nintedanib is not permitted throughout the study, given lack of adequate safety information on this drug combination. *Patients in Cohort B may initiate other approved therapies in the absence of disease progression if pirfenidone is stopped because of safety considerations.* The Principal Investigator should notify the Medical Monitor of proposed changes in concomitant IPF therapy prior to starting rescue therapy for patients in either Cohort A or Cohort B throughout the study.

Patients who start rescue therapy must begin appropriate monitoring per the prescribing information for that therapy. All safety laboratory assessments, including those required for the prescribed rescue medication, should be analyzed by the central laboratory utilized for the GB28547 clinical study.

4.4.2 Prohibited Therapy

- Chronic treatment with any of the following within 4 weeks or five half-lives prior to screening (whichever is longer) to the end of the placebo-controlled period (Day 365, Visit 16)
 - Immunosuppressive or immunomodulatory therapies (e.g., azathioprine, cyclosporine A, cyclophosphamide, D-penicillamine, interferon-gamma, tumor necrosis factor- α antagonists)
 - Cytotoxic drugs (e.g., colchicine) if used for IPF indication
 - Pirfenidone (exclusion limited to Cohort A)
 - N-acetylcysteine
 - Pulmonary hypertension therapies (e.g., endothelin receptor antagonist, phosphodiesterase type-5 inhibitor, riociguat, prostacyclin, or prostacyclin analogue)
 - Tyrosine kinase inhibitors including nintedanib for Cohort A and Cohort B
 - Warfarin or other anticoagulant therapy if given for IPF indication
 - Any unlicensed therapy given for the indication of IPF
 - Any investigational agent

- Chronic oral corticosteroid therapy is not permitted within 4 weeks prior to screening (Visit 1), during screening and *run-in*, or throughout the study period.
- N-acetylcysteine or IPF therapy approved by local regulatory authorities can be initiated in the event of disease progression as per Section 4.4.1.2. *Patients in Cohort B may initiate other approved IPF therapies in the absence of disease progression if pirfenidone is stopped because of safety considerations.*
- No other therapies for IPF can be started at any time during the study.

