At the end of the screening period, and applicable qualifying pirfenidone titration run-in period for patients requiring pirfenidone titration, eligible patients will be randomized in a 1:1 ratio within each cohort to double-blind treatment with SC lebrikizumab 250 mg or placebo. Dynamic hierarchical randomization will be performed centrally and stratified by region (United States, Europe/Canada, and other), lung function (FVC $< 50\%$, 50% to 75% , $> 75\%$ predicted), and serum periostin concentration (< 50 ng/mL, ≥ 50 ng/mL) in each cohort.

Study drug will be administered by SC injection every 4 weeks, with the first injection occurring at the randomization visit (Day 1, Visit 2). Patients will continue to receive blinded study treatment every 4 weeks during the placebo-controlled treatment period for a total of 13 doses/26 injections of blinded treatment. Safety, efficacy, and patient reported outcomes will be assessed throughout the placebo-controlled study period as detailed in the schedule of assessments (see [Appendix 1](#) and [Appendix 3](#)). The primary efficacy endpoint is the absolute change from baseline to Week 52 in percentage of predicted FVC.

[figure not shown]
Patients in Cohort A who complete or exceed the minimum 52-week blinded placebo-controlled period (i.e., patients who have not prematurely discontinued study treatment) may continue into the 52-week open-label lebrikizumab treatment period. All patients who continue into the 52-week open-label lebrikizumab treatment period will receive SC lebrikizumab at a dose of 250 mg every 4 weeks. Exclusion of background IPF treatment is not required during this study period. During the open-label lebrikizumab period, at the investigator's discretion, a patient can start background therapy, including use of pirfenidone or other treatment, provided that it is an approved therapy for IPF in the applicable region (e.g., European Union, Canada, Mexico, Peru, or Japan) (see Section 4.4.1.2). Safety and efficacy will be measured as detailed in the schedule of assessments (see [Appendix 2](#)).

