4.1.2 Exclusion Criteria

Patients who meet any of the following criteria will be excluded from study entry:

- History of a severe allergic reaction or anaphylactic reaction to a biologic agent or known hypersensitivity to any component of the lebrikizumab injection
- Evidence of other known causes of ILD (e.g., domestic and occupational environmental exposures, connective-tissue disease [CTD], and drug toxicity)
- Lung transplant expected within 12 months of screening
- Evidence of clinically significant lung disease other than IPF (e.g., asthma or COPD)
- Post-bronchodilator forced expiratory volume in 1 second (FEV₁)/FVC ratio < 0.7 at screening
- Positive bronchodilator response evidenced by an increase of $\geq 12\%$ predicted and 200 mL increase in either FEV₁ or FVC

- Any clinically significant medical disease (other than IPF) that is associated with an expected survival of < 12 months, likely to require a change in therapy during the study, or likely to impact the ability of the patient to participate in the study in the opinion of the investigator, or impact the study efficacy or safety assessments
- Requirement for continuous medical care and assistance or limited ability to self-care that would impact the ability of patient to participate in the study or to perform the study-related assessments
- Class IV New York Heart Association chronic heart failure or historical evidence of left ventricular ejection fraction < 35%
- Hospitalization due to an exacerbation of IPF within 4 weeks prior to or during screening
- Known current malignancy or current evaluation for a potential malignancy
- Major episode of infection requiring any of the following:
 - Admission to the hospital for ≥ 24 hours within 4 weeks prior to screening or during screening and run-in period
 - Treatment with antibiotics (IV, IM, oral, or inhaled) within 4 weeks prior to screening or during screening and run-in period
- An active upper or lower respiratory tract infection occurring at any time within the screening period prior to the randomization visit (Visit 1 to Day 1, Visit 2)
- *Listeria monocytogenes* infection or active parasitic infection within 6 months prior to Day 1, Visit 2
- Active tuberculosis requiring treatment within 12 months prior to screening
- Known immunodeficiency, including but not limited to HIV infection
- Past use of any anti-IL-13 or anti-IL-4/IL-13 therapy, including lebrikizumab

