 - Patients participating in a clinical trial that has not been unblinded should be assumed to have received the active drug
- Evidence of acute or chronic hepatitis or known liver cirrhosis
- AST, ALT, or total bilirubin elevation $\geq 2.0 \times$ the upper limit of normal during screening
- Clinically significant abnormality on ECG at screening or laboratory tests (hematology, serum chemistry, and urinalysis) that, in the opinion of the investigator, may pose an additional risk in administering study drug to the patient
- Receipt of a live/attenuated vaccine within the 4 weeks prior to Visit 1
- Chronic treatment with any of the following within 4 weeks or five half-lives prior to screening (whichever is longer) to the end of the placebo-controlled period (Day 365, Visit 16):
 - Immunosuppressive or immunomodulatory therapies (e.g., azathioprine, cyclosporine A, cyclophosphamide, D-penicillamine, interferon-gamma, tumor necrosis factor- α antagonists)

Cytotoxic drugs (e.g., colchicine) if used for IPF indication

Pirfenidone (Exclusion Limited to Cohort A)

N-acetylcysteine

Pulmonary hypertension therapies (e.g., endothelin receptor antagonist, phosphodiesterase type-5 inhibitor, riociguat, prostacyclin or prostacyclin analogue)

Tyrosine kinase inhibitors including exclusion of nintedanib for Cohort A and Cohort B

Warfarin or other anticoagulant therapy if given for IPF indication

Any unlicensed therapy given for the indication of IPF

Any investigational agent

- Chronic oral corticosteroid therapy is not permitted within 4 weeks prior to screening (Visit 1), during screening and run-in, *or throughout the study* period
- History of alcohol, drug, or chemical abuse that would impair or risk the patient's full participation in the study, in the opinion of the investigator
- Female patients of reproductive potential who are not willing to use a highly effective method of contraception (e.g., contraceptive pill or transdermal patch, spermicide and barrier [i.e., condoms], intrauterine device, implants for contraception, injections for contraception [with prolonged release], hormonal vaginal device, sterilization, surgical tubal ligation) for the duration of the study and for at least 18 weeks after the last dose of lebrikizumab or placebo study treatment) (see [Appendix 9](#))
- Pregnant or lactating
- Body weight < 40 kg

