4.3.3 Dosage, Administration, and Compliance

4.3.3.1 Lebrikizumab and Placebo (Cohort A)

Patients in Cohort A and Cohort B who meet all eligibility criteria will be randomly assigned to receive lebrikizumab 250 mg or placebo Q4W for the 52-week placebo controlled period.

Treatment with lebrikizumab or placebo will be by SC injection in the arm, thigh, or abdomen. All patients will receive a total of two injections per dosing visit. Each injection should be administered in a separate location at least 10 cm from the other injection site at each dosing visit. Study sites will be asked to record each injection site. Patients will be monitored for a minimum of 1 hour after dosing for the first three treatment visits and for 30 minutes for all subsequent treatment visits. Each patient will receive a minimum of 13 doses (2 injections per dose) of study treatment during the placebo-controlled, blinded, study treatment period. Patients in Cohort A who enrolled in the study prior to this amendment may receive up to 31 doses of blinded study treatment based upon previous version of this protocol. No dosage modification is permitted during the study.

Patients in **Cohort A** will receive an additional 52 weeks of open-label lebrikizumab (13 doses) in the open-label lebrikizumab treatment period after completion of the placebo controlled period.

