In Phase III studies of patients with moderate-to-severe asthma, herpes infections including herpes zoster (shingles) were reported in 2.0% of patients who were treated with lebrikizumab compared with 0.7% of patients who were treated with placebo. In a Phase II study of patients with moderate-to-severe atopic dermatitis, herpes infections including herpes zoster (shingles) were reported in 3.8% of the patients who were treated with lebrikizumab. None of the herpes infections that were reported, including herpes zoster, required a hospital admission. In Cohort A of Study GB28547, herpes viral infections in patients were reported but there were no imbalances noted between

patients who were treated with lebrikizumab and patients who were treated with placebo. Refer to the Lebrikizumab IB for more detail.

Patients with a history of active tuberculosis requiring treatment within the 12 months prior to screening will be excluded from study participation. Patients who have completed treatment for tuberculosis at least 12 months prior to Visit 1 and have no evidence of recurrent disease are permitted.

In addition, patients will be excluded from study participation if they experience an episode of infection requiring hospitalization for ≥ 24 hours or treatment with antibiotics (IV, oral, or inhaled) within 4 weeks prior to Day 1 or during screening.

Patients with an active upper or lower respiratory tract infection occurring at any time within the screening period prior to the randomization visit (Visit 1 to Day 1, Visit 2) are excluded, even if the infection did not require antibiotics.

All infections that occur during the study, including non-serious infections such as viral upper respiratory infections, should be reported immediately to the Sponsor as adverse events of special interest and as serious adverse events, if appropriate. Detailed information with regard to parasitic or other infections that occur during the study will be collected, regardless of whether the events are serious (see Section 5.2.2) or non-serious (see Section 5.2.3).

Given that blockade of the effector function of IL-13 constitutes immune modulation, patients will be excluded if they are receiving other immunomodulatory therapies (because of the uncertainty of the combined effect of lebrikizumab with such therapies) or if they have a known immunodeficiency, including but not limited to HIV infection.

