6MWT=6-minute walk test; ATAQ-IPF=A Tool to Assess Quality of Life in IPF; Borg CR10=Borg Category Ratio 10 Scale[®]; DL_{CO}=diffusion capacity of the lung for carbon monoxide; ECG=electrocardiogram; EOT=end of treatment; EQ-5D=EuroQol 5-Dimension Questionnaire; ET=early termination; HRCT=high-resolution computed tomography; IPF=idiopathic pulmonary fibrosis; Rand.=randomization; SGRQ=St George's Respiratory Questionnaire; UV=unscheduled visit.

^a Patients who discontinue study drug are encouraged to remain in the study and complete all scheduled assessments. If this is not feasible, the patient should enter and complete the safety follow-up period or the early termination assessments, unless consent has been withdrawn. If a patient is unable or unwilling to complete the assessment for 6MWT and/or the qHRCT substudy assessment this will not be considered a protocol deviation.

^b Patients who enter the open label lebrikizumab treatment period should complete Day1 OL visit 35 on the same day.

Appendix 1

Schedule of Assessments: Screening and Placebo Controlled Treatment Period - Cohort A (cont.)

- ^c Informed consent may be obtained on the day of Visit 1 or prior to visit 1 at the discretion of the investigator. The informed consent process must be completed before initiating any Visit 1 assessments.
- ^d Record abnormalities observed at baseline on the Medical History and Baseline Conditions eCRF. New or worsening abnormalities should be recorded on the Adverse Event eCRF.
- ^e Respiratory rate, pulse rate, systolic and diastolic blood pressure while the patient is in a seated position, and temperature.
- ^f ECGs should be performed prior to any scheduled study procedures (e.g., vital sign measurements, blood draws, and study drug administration, if applicable).
- ^g Both pre- and post-bronchodilator testing are required at screening, but only pre-bronchodilator pulmonary function test is required throughout other study visits.
- ^h A Multidisciplinary Discussion of Diagnosis (MDD) based on 2011 ATS/ERS/JRS/ALAT guidelines will be utilized to finalize the diagnosis in the event the initial central review outcome results for HRCT and SLB are disparate (inconsistent with usual interstitial pneumonitis (UIP)/definite UIP).

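### Cohort A patients who take pirfenidone fall outside the CYP1A2-inhibitor and ciprofloxacin rules, and the immunomodulator ban ends on the day their open-label lebrikizumab starts

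*Combined protocol and SAP*

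**What the plan says.** **Pirfenidone interactions.** Protocol Section 4.4.2.1 is limited to Cohort B by its title. It prohibits strong CYP1A2 inhibitors and tobacco. If high-dose ciprofloxacin cannot be avoided, it cuts pirfenidone to two capsules three times a day, citing the package insert. Its window closes at the end of safety follow-up. Section 4.1.2.1 and the synopsis repeat the inhibitor and tobacco items, again for Cohort B only.

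Cohort A may also receive pirfenidone. Section 4.4.1.2 allows it as rescue after confirmed progression, and in the open-label period without progression. Section 3.1.1 says of that period: "Exclusion of background IPF treatment is not required during this study period".

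**Immunomodulators.** Section 4.4.2 bars a list of chronic therapies, immunosuppressive and immunomodulatory drugs among them, over a window that runs from four weeks or five half-lives "prior to screening (whichever is longer) to the end of the placebo-controlled period (Day 365, Visit 16". Section 4.1.2 and the synopsis give the same end point ("to the end of the placebo-controlled period (Day 365, Visit 16").

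For Cohort A, footnote b of protocol Appendix 1 adds: "Patients who enter the open label lebrikizumab treatment period should complete Day1 OL visit 35 on the same day". Section 4.3.3.1 says that these patients "will receive an additional 52 weeks of open-label lebrikizumab (13 doses". Section 5.1.1.3 excludes patients already on other immunomodulators "because of the uncertainty of the combined effect of lebrikizumab with such therapies".

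**The concern.** Each rule stops short of patients to whom the same hazard applies.

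A CYP1A2 inhibitor acts on pirfenidone whichever cohort the patient is in. As written, giving one to a Cohort B patient on pirfenidone is a protocol deviation, and giving it to a Cohort A patient on pirfenidone is not.

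On immunomodulators, the uncertainty about combining them with lebrikizumab does not end at Week 52. While the ban is in force, 1:1 randomization means that about half of Cohort A is on placebo. It lapses when every continuing patient goes onto active drug, some for the first time.

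The stake is the safety of individual patients and the clarity of the rules for sites. The Week 52 comparison, the sample size and the error rate are not affected.

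**Working it through.** The plan states no figure to reproduce. The check compares the texts, with some date arithmetic.

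**Pirfenidone rules, by cohort**

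| Rule | Cohort B | Cohort A on pirfenidone |
|---|---|---|
| Liver tests and dose changes (5.1.4.1) | applies | applies, stated expressly |
| Toxicity monitoring per package insert (5.1.4) | applies | applies |
| Strong CYP1A2 inhibitors barred (4.4.2.1) | applies | not stated |
| Ciprofloxacin dose reduction (4.4.2.1) | applies | not stated |

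Section 5.1.4.1 takes rules from the package insert and applies them to anyone starting pirfenidone, in either cohort. The authors therefore did extend a label rule to Cohort A when they meant to. Section 4.4.2.1 has no such sentence. The ciprofloxacin rule is a material dose change: from 9 capsules a day to 2 × 3 = 6, or from 9 × 267 = 2403 mg to 6 × 267 = 1602 mg.

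**Immunomodulator window**

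1. The ban ends on Day 365, Visit 16 (4.4.2). Open-label Day 1, Visit 35, is the same day (Appendix 1, footnote b).
2. The open-label period runs from Day 365 to Day 729 (Appendix 2): 729 − 365 = 364 days, and 364 / 7 = 52 weeks, with 13 planned doses. The ban covers none of the time after the first open-label dose.
3. A patient who has kept to the protocol has by then been off the listed drugs for at least 4 weeks before screening, plus (28 ± 14) / 7 = 2 to 6 weeks of screening, plus 52 weeks. That is 58 to 62 weeks, so the gap concerns new starts only.
4. Other rules narrow it further. Chronic oral corticosteroids are barred throughout the study (4.4.2). For IPF, apart from the therapies that are expressly allowed, "No other therapies for IPF can be started at any time during the study". A non-IPF disease "likely to require a change in therapy during the study" is an exclusion (4.1.2).
5. What is left is a newly started, chronic, non-steroid immunomodulator for a non-IPF disease. It is barred before Day 365, because only 3 of the 9 listed items are limited to IPF use (cytotoxics, anticoagulants, unlicensed therapy) and this item is not one of them. After Day 365 no stated rule bars it.

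**Other controls.** Section 4.6.1.1 lists three mandatory reasons to stop study drug: pregnancy, a serious hypersensitivity-type reaction, and malignancy. Starting an immunomodulator is not one. The notice to the Medical Monitor in Section 4.4.1.2 concerns changes in IPF therapy. It would not be triggered by a non-IPF immunomodulator, or by an inhibitor or antibiotic added after pirfenidone was under way.

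**The case against.** The best case for the plan has four parts.

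- **The Day 365 end point may be deliberate.** The Section 4.4.2 list is mixed and closes with the placebo-controlled period, which suits protecting the comparison. Section 3.2.3 gives confounding as the reason for excluding other IPF therapies from Cohort A. A reader might infer that the plan contradicts its own stated reason for the window. The documents do not support that: Section 5.1.1.3 is worded as an entry exclusion and never explains why the window closes at Day 365. What stands against the plan is that the same uncertainty applies on open-label drug, and the only relaxation explained for that period is for IPF therapy.
- **The label already governs pirfenidone in Cohort A.** Section 5.1.4 requires monitoring consistent with package inserts, Section 4.4.1.2 requires it for rescue therapy, and the ciprofloxacin rule itself comes from the insert. A reader might infer that Cohort A patients have no protection, which would be wrong. But these provisions require monitoring. They do not carry over the express ban or the dose cut, which the sponsor chose to write out for Cohort B.
- **Discretion exists.** Under Section 4.6.1 the investigator or the sponsor may stop study drug to protect a patient. This helps, but it is not a prohibition.
- **The reach is limited.** Cohort A enrollment was complete by 8 April 2015 (SAP Section 2), and the last visit was due at most 118 weeks later (protocol Section 3.2), about July 2017. Version 7 postdates the August 2016 futility analysis (Section 1.4), so rewording it reaches only the tail of open-label dosing. This stands, and it limits the urgency.

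It can also be said that ending the extended immunomodulator ban at end of treatment is line-drawing, since drug persists into follow-up. That is fair. The plan already accepts the same residual exposure in Cohort B.

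**Conclusion.** Both gaps are present in the current text, and closing them would be a cheap improvement to safety conduct. The pirfenidone gap is the main one: the strong-inhibitor ban and ciprofloxacin rule follow the cohort when the hazard follows the drug. The immunomodulator gap is secondary. It lasts 52 weeks and 13 planned doses, for Cohort A patients who continue, and is confined to new, chronic, non-steroid, non-IPF drugs.

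The documents do not say how many Cohort A patients met either situation, so the frequency is unknown and no harm can be claimed. The Cohort A infection counts in Section 5.1.1.3 (51 of 78, 65.4%, against 41 of 76, 53.9%) might be read as evidence of harm from this gap. They are not: they compare the randomized arms, and the protocol attributes the difference mainly to urinary infections, with predisposing risk factors in all the lebrikizumab patients affected.

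The conclusion rests on reading Section 4.4.2.1 as limited by its title, and on no separate instruction to sites having closed the gap.

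**What to change.** 1. **Section 4.4.2.1.** Leave the Cohort B text and window as they are. Add one sentence saying that the strong CYP1A2 inhibitor ban and the ciprofloxacin rule also apply to any Cohort A patient while taking pirfenidone, on the pattern of Section 5.1.4.1. Replacing the whole section with a rule tied to pirfenidone use in either cohort would be a mistake, because it could shorten Cohort B's window, which now runs to the end of safety follow-up. Handle tobacco in Cohort A through the prescribing information, since only Cohort B was screened for it (4.1.2.1).
2. **Sections 4.4.2 and 4.1.2 and the synopsis.** Take the immunosuppressive/immunomodulatory item out of the shared list and give it its own window: to Day 365, Visit 16, or, for Cohort A patients who continue, to the end of open-label lebrikizumab treatment. Cohort B's window does not change.

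The cost is a few words in four places. The downside is that a few open-label patients may have to choose between a listed drug and continued lebrikizumab.
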